5.7 Pharmacokinetic Parameters

Not applicable.

5.8 Other Parameters

The end users who need to be assessed prior to use of Prismocitrate 18 in the clinical trial setting (as delegated by an investigator) will be comprised of physicians, nurses, and other clinicians who may be part of prescribing, initiating, or modifying treatment during the 120 hours Evaluation period. A descriptive summary of training results on administration of Prismocitrate 18 will be provided in the Clinical Study Report following completion of the study.

5.9 Completion and Discontinuation

The number of completed and discontinued subjects along with reasons for discontinuation will be summarized. Individual reasons for study discontinuation will be listed.

6. STUDY POPULATIONS

The following inclusion and exclusion criteria were applied in the selection of study patients:

Inclusion Criteria

- 1. Patient, or legally-authorized representative, has signed a written ICF.
- 2. Patient must be receiving medical care in an intensive care unit (ICU) [e.g., medical ICU, surgical ICU, cardiothoracic ICU, Trauma ICU, Mixed ICU, other].
- 3. Patient age \geq 18 years.
- 4. Adult patients with AKI or other serious conditions who require treatment with CRRT
- 5. Patients are expected to remain in the ICU and on CRRT for at least 72 hours after randomization.
- 6. Patients already receiving standard-of-care CRRT must be randomized within 24 hours of initiation of their standard-of-care CRRT.

Exclusion Criteria

1. Patients requiring systemic anticoagulation with antithrombotic agents for reasons other than CRRT. The exception is patients receiving subcutaneous heparin for

- deep vein thrombosis prophylaxis according to institutional practice or patients on aspirin may be enrolled.
- 2. Patients in whom citrate anticoagulation is contraindicated such as patients with a known allergy to citrate or who have experienced adverse events associated with citrate products including patients with a prior history of citrate toxicity or patients with uncorrected severe hypocalcemia (whether in the context of current citrate administration or due to the underlying disease state).
- 3. Patients who are not candidates for CRRT.
- 4. Patients who are receiving extracorporeal membrane oxygenation (ECMO) therapy.
- 5. Patients with severe coagulopathy [i.e., platelets < 30,000/mm³, international normalized ratio (INR) > 2, partial thromboplastin time (PTT) > 50 seconds]; including severe thrombocytopenia (platelets < 30,000/mm³), HIT (hereditary idiopathic thrombocytopenia), ITP (idiopathic thrombocytopenia purpura), and TTP (thrombotic thrombocytopenia purpura) should not be enrolled in the trial.
- 6. Patients with fulminant acute liver failure or acute on chronic liver failure as documented by a Child-Pugh Liver Failure Score > 10.
- Patients with refractory shock associated with persistent, worsening lactic acidosis (lactate >4 mmol/L). However, patients with improving subsequent serum lactate levels may be enrolled.
- 8. Patients unlikely to survive at least 72 hours.
- 9. Female patients who are pregnant, lactating, or planning to become pregnant during the study period. Note: A female patient of childbearing potential, defined as a woman less than 55 years old who has not had partial or full hysterectomy or oophorectomy, must have a negative serum beta human chorionic gonadotropin (β-hCG) pregnancy test during the screening period (after consent and prior to randomization) and before CRRT treatment begins. A female patient of childbearing potential must use medically acceptable means of contraception during their participation in the study.
- 10. Patients who are currently participating in another interventional clinical study.
- 11. Patients with a medical condition that may interfere with the study objectives.

6.1 Subject Disposition

The number of study patients included in the two (2) different analysis sets will be summarized by treatment group.

6.2 Analysis Populations

Statistical analyses will be carried out based on two (2) different analysis sets:

6.2.1 Full Analysis Set (FA)

The Full Analysis Set (FA) will include all randomized patients who received any study treatment for any period of time. The Full Analysis set will be analyzed based upon the subjects randomized treatment.

6.2.2 Per-Protocol Analysis Set (PP)

The Per-Protocol Analysis Set (PP) defines a subset of the FA including patients who

- fulfill all inclusion criteria
- do not meet any of the exclusion criteria
- were randomized and treated according to the randomization scheme
- received at least 80% of their prescribed CRRT dose
- do not have major protocol deviations that might impact the assessment of the primary endpoint (e.g., mechanical malfunction of the machine)
- have available survival data for extracorporeal circuit life of at least one circuit
 (i.e., time to occurrence of Prismaflex System alarms/conditions as outlined in
 Section 5.5.1 Primary Efficacy Endpoint, or censored circuit life if no system
 alarms/conditions occurred until the circuit was used for 72 continuous hours or if
 CRRT was stopped during the evaluation period for reasons other than system
 alarms/conditions).

The Per Protocol Set will be analyzed based upon the subjects randomized treatment.

6.3 Protocol Deviations

Protocol Deviations will be classified as major and minor deviations.

Subjects with any major protocol deviation that may impact the primary endpoints will be excluded from the per-protocol analysis set, including but not limited to the following:

- Violations of inclusion and/or exclusion criteria
- Use of prohibited medication known to influence the primary endpoint
- Randomization or treatment errors
- Improper administration of study product
- Improper assessment of the primary endpoint
- Any other protocol deviations that may impact the primary endpoints

Frequencies of protocol deviations will be presented by study site and across all study sites on a deviation as well as on a subject basis.

7. SUBGROUPS

No specific subgroup analyses are planned for this study.

8. STATISTICAL ANALYSIS

Unless specifically stated otherwise, throughout the document, Prismocitrate 18 relates to the study group receiving CRRT with Prismocitrate 18 solution whereas Control relates to the study group receiving CRRT with no systemic anticoagulation before a potential cross-over of treatments.

8.1 General/Types of Analyses

Unless otherwise specified, treatment effects will be evaluated on the basis of a 2-sided significance level of 0.050 (when rounded to 3 decimal places). All analyses will be performed using Statistical Analysis Software (SAS®), SAS/GRAPH® and SAS/STAT® software, Version 9.2 of SAS for Windows, Copyright© 2018 SAS Institute Inc., on a Microsoft Windows Server. SAS and all other SAS Institute Inc. product or service names are registered trademarks or trademarks of SAS Institute Inc., Cary, NC, USA¹0.

8.2 Handling of Missing Data

Missing data will neither be estimated nor replaced. No imputation of missing values will be performed. The survival type nature of data of the primary efficacy endpoint allows inclusion of any available information on extracorporeal circuit life in the statistical analysis according to the defined analysis populations.

8.3 Interim Analysis

A single interim analysis will be conducted when 50% of patients have completed treatment. The purpose of the interim analysis is to evaluate the primary efficacy

endpoint for overwhelming efficacy, or the need to adjust the sample size. Sample size re-estimation at the interim analysis will be based on Fisher's criterion (Fisher's combination test). For further details please refer to Section 13.5 Interim Analysis.

8.4 Pooling Strategy for Study Sites

Data will be pooled across all study sites unless indicated otherwise. Protocol deviations will be presented in total across all study sites and split by study sites.

8.5 Blood Sampling Schedule and Additional Blood Draws

The compliance of the study sites with the specified blood sampling schedule will be analyzed using frequencies and percentages. The number of subjects with blood draws inside and outside the defined blood sampling time window will be summarized per blood sampling time point and study site.

Laboratory measurements resulting from additional blood draws will not be presented in descriptive summaries, though will be listed and used in mixed-effects model repeated measures (MMRM) analysis.

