5.2.3 Monitoring of Therapy

Systemic iCa levels will be measured at baseline, initiation, and systemic and post-filter blood iCa levels will be measure 1 hour after initiation of study CRRT (post-randomization) and then every 6 hours thereafter and at 120 hours or end of Treatment Period. The pH and bicarbonate should be measured at baseline, initiation, and every 6 hours during the 120 hour Treatment Period and at 120 hours or end of Treatment Period. Health care professionals managing the patient should be instructed to notify the clinician immediately if the serum pH is < 7.20 or > 7.45, serum bicarbonate is < 15 or > 35 mmol/L, and/or the systemic blood iCa is < 0.9 or > 1.3 mmol/L.

Citrate metabolism may be impaired in patients with moderate to severe liver failure. The additional steps outlined below are needed to monitor specifically for the potential development of citrate accumulation, not only in these patients but in the entire study

population. Blood total calcium concentrations will be measured at baseline, initiation, 1 hour and every 6 hours during the 120 hour Treatment Period and at 120 hours or end of the Treatment Period from the initiation of study CRRT. In conjunction with simultaneous systemic iCa concentrations, the total calcium/iCa ratio (both measurements in mmol/L) will be determined as an indicator of citrate accumulation and health care professionals managing the patient should be instructed to notify the clinician for any value above 2. 1. Moreover, based on the clinical judgement of the managing physician, this threshold value should also prompt an immediate CRRT prescription change designed to correct the metabolic disturbance. One of the following prescription changes should occur:

- Decrease in the Prismocitrate infusion rate; or
- Increase in the BFR; or
- Increase in the dialysate flow rate

The effect of one of these changes should be assessed with ongoing monitoring of relevant clinical and laboratory parameters - if improvement does not occur within two (2) hours, the Prismocitrate infusion should be stopped.

When a total calcium/iCa ratio of more than 2.1 is reported, any one of the following abnormalities reported concurrently should heighten the clinical suspicion of citrate accumulation and reinforce the need to undertake the steps outlined above:

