8.6 Safety Endpoints

Analysis of safety endpoints will be carried out on the FA Set based on the actual treatment groups for the following parameters:

- 1. A MMRM analysis will be used to evaluate differences between treatment groups in the change from baseline in serum bicarbonate and pH that are collected every 6 hours from the initiation of study CRRT during the 120 hour Treatment Period and at 120 hours or end of the Treatment Period. Frequencies and percentages will be provided for pH < 7.2 by time point and treatment group (thresholds indicative of metabolic acidosis).
- 2. A MMRM analysis will be used to evaluate differences between treatment groups in the change from baseline in blood total calcium concentrations that are assessed at 1 hour and every 6 hours from the initiation of study CRRT during the 120 hour Treatment Period and at 120 hours or end of the Treatment Period.
- 3. A MMRM analysis will be used to evaluate differences between treatment groups in the change from baseline in serum electrolytes (sodium, potassium, chloride, phosphate, and magnesium) that are collected every 6 hours from the initiation of study CRRT during the 120 hour Treatment Period and at 120 hours or end of the Treatment Period.

- 4. A descriptive summary of the total calcium/systemic iCa ratio as assessed at baseline, at initiation of study CRRT, 1 hour and every 6 hours from the initiation of study CRRT during the 120 hour Treatment Period and at 120 hours or end of the Treatment Period will be provided by treatment group. Frequencies and percentages will be provided for total calcium/systemic iCa ratio > 2.1 by time point and treatment group (threshold suggestive of citrate accumulation). Frequencies and percentages will be provided for anion gap > 11 mmol/L by time point and treatment group (threshold indicative of metabolic disturbance) as well as for base excess < -5 mmol/L.
- 5. A descriptive summary of the number, location, and duration of bleeding events along with the estimated blood loss during the 120 hour Treatment period will be provided by treatment group. The number and type of blood transfusion along with the number of units infused will also be summarized.
- 6. An analysis of covariance (ANCOVA) model will be used to evaluate differences between treatment groups in the change from baseline to final measurement in laboratory and vital signs measurements.

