13.3 Secondary Analysis

A descriptive summary of systemic and post-filter blood iCa²⁺ concentrations as assessed at baseline (systemic only), 1 hour and every 6 hours during the 120 hours evaluation period and at 120 hours or end of the Evaluation period will be provided by treatment group. This summary will use the number of subjects n, mean, standard deviation, minimum, median and maximum. Changes from baseline will be analyzed by the number of subjects n, mean and standard deviation and t-test or Wilcoxon rank sum test, as applicable.

The individual blood iCa²⁺ concentrations will further be displayed graphically over time for each of the two treatment groups.

A MMRM analysis will be deployed to evaluate differences between treatment groups in blood i Ca^{2+} concentrations that are collected at baseline, 1 hour and every 6 hours during the 120 hours Evaluation period and at 120 hours or end of the Evaluation period from the initiation of CRRT. The model will include the illness severity score APACHE II, baseline i Ca^{2+} concentration, treatment group and time point as fixed effects, and an interaction between time point and treatment group will be included in the model only if treatment effects differ statistically significantly over time (p < 0.01).

In addition, frequencies and percentages will be provided for $iCa^{2+} < 1.1 \text{ mmol/L}$ by time point and treatment group (threshold indicative of decrease in iCa^{2+} despite adequate calcium compensation).

Daily delivered dose and overall delivered dose (both in mL/kg/hour) will be summarized using the number of subjects n, mean, standard deviation, minimum, median and maximum, as applicable. Treatment exposure will be analyzed carrying out the same descriptive summary for the percentages of the prescribed dose actually administered to the patient.

Effluent rate is considered an appropriate surrogate for the CRRT dose. Therefore, prescribed and delivered CRRT dose will be derived as follows based on the University of Alabama at Birmingham Continuous Venovenous Hemodiafiltration Protocol¹² used in the study:

$$Q_E = Q_{PBP} + Q_D + Q_{FR} + Q_R$$

where Q_E is the effluent rate (mL/hour),

Q_{PBP} is the pre-blood pump infusion rate which is the Prismocitrate 18 flow rate (mL/hour),

Q_D is the dialysate flow rate (mL/hour),

Q_{FR} is the patient fluid removal rate (mL/hour), and

Q_R is the post-filter replacement fluid rate (mL/hour).

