14.3 Serum Bicarbonate, pH, Blood Total Calcium and Serum Electrolytes

Serum bicarbonate, pH (ABG), blood total calcium concentrations and serum electrolytes (sodium, potassium, chloride, phosphate, magnesium) will be analyzed in the exact same manner as blood iCa²⁺ concentrations.

Along the lines of Section 13.3 Secondary Analysis descriptive summaries will be carried out for each parameter at the different assessment time points, and changes from baseline will be analyzed. A MMRM analysis will be deployed for the different parameters following the description under Section 13.3.

The total calcium/iCa²⁺ ratio will only be summarized descriptively. Frequencies and percentages will be provided for pH < 7.2 by time point and treatment group (threshold indicative of metabolic acidosis). Frequencies and percentages will further be provided for total calcium/iCa ratio > 2.1 by time point and treatment group (threshold suggestive of citrate accumulation) as well as for anion gap > 11 mmol/L (threshold indicative of metabolic disturbance) and base excess < -5 mmol/L.

Complete blood count and blood lactate measurements obtained at screening will be listed by patient.

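### SAP 8.5 keeps additional blood draws out of the descriptive summaries and no any-time table is planned, so the number of patients who ever crossed a metabolic safety limit cannot be read from the tables

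*SAP*

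**What the plan says.** SAP 8.5 sets the rule for blood taken outside the schedule: "Laboratory measurements resulting from additional blood draws will not be presented in descriptive summaries". The second half of that sentence keeps a place for these values elsewhere: "though will be listed and used in mixed-effects model repeated measures (MMRM) analysis". It does not define an additional draw. For example, it does not say whether a scheduled sample taken outside its window counts as one.

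The threshold reporting is set elsewhere:

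- **Ratio.** SAP 14.3 says that the total calcium/iCa "ratio will only be summarized descriptively", so no model is fitted to it. Protocol 8.6 adds: "Frequencies and percentages will be provided for total calcium/systemic iCa ratio > 2.1 by time point and treatment group".
- **iCa below 1.1 mmol/L.** SAP 13.3 gives the frequency by time point. iCa also has an MMRM.
- **pH below 7.2, anion gap above 11 mmol/L, base excess below -5 mmol/L.** SAP 14.3 gives frequencies, also by time point in Protocol 8.6 for pH and anion gap. pH has an MMRM in SAP 14.3. The SAP table lists add MMRM tables for anion gap and base excess.

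These counts are Tables 14.2.12.1 to 14.2.12.5. Neither SAP table list names a laboratory table of patients beyond a limit at any time, or of worst values. Protocol 2.2 and SAP 4.2 single out the ratio, with anion gap, base excess and pH, as the measures of citrate accumulation.

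**The concern.** Samples outside the schedule are often taken because something looks wrong. Protocol 5.2.3 makes them foreseeable. After a ratio above 2.1 it asks for a prescription change and continued monitoring, and then: "if improvement does not occur within two (2) hours, the Prismocitrate infusion should be stopped". Scheduled samples are 6 hours apart.

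An exceedance that shows only on such a sample has no place in a by-time-point table. For the ratio, the leading measure of the risk that the protocol names, there is no model either. By-time-point percentages also do not show whether the same few patients or many different patients are affected. The clinical study report could then be unable to say how many patients ever showed the protocol's own signal of citrate accumulation.

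**Working it through.** The plan gives no figure of its own on this point, so there is nothing to reproduce. The check has three parts.

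**1. Where can a value from an additional draw appear?**

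| Parameter | Threshold table (by time point) | MMRM | Listing |
|---|---|---|---|
| Total calcium/iCa ratio | no | none planned | yes |
| iCa | no | yes (SAP 13.3) | yes |
| pH | no | yes (SAP 14.3) | yes |
| Anion gap, base excess | no | yes (table lists) | yes |

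Two rules can let a non-scheduled value into a summary. Note c to SAP Table 2 uses the latest treatment-period value when the termination sample is missing, and does not restrict it to scheduled draws. Protocol 5.2 makes a corrected iCa the initiation value in the Prismocitrate 18 arm. A separate route is the AE tables. Under Protocol 6.10 a laboratory abnormality is an AE if it needs intervention, leads to discontinuation, or passes a standard-of-care limit, whichever draw found it. SAP 14.1 then counts subjects by preferred term.

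**2. How often would a short excursion fall between scheduled draws?** iCa, total calcium and the ratio are sampled at 1 h and then every 6 h to 120 h: 1 + 120/6 = 21 times. For an excursion of D hours starting at a random moment, the chance of overlapping a scheduled draw is min(1, D/6). With windows of ±1 h, neighbouring draws remain at least 4 h apart, so D/6 still holds on average up to D = 4. The durations are assumptions.

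| D (assumed) | D/6 | Simulation, starts after hour 6 |
|---|---|---|
| 1 h | 0.17 | 0.16 |
| 2 h | 0.33 | 0.32 |
| 4 h | 0.67 | 0.66 |
| 6 h | 1.00 | 1.00 |

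This shows that short excursions can be missed. It does not show how many are. If an assumed 10% of 80 patients in an arm (8 patients) ever crossed a limit, and an assumed share f of them did so only on additional draws, a scheduled-only count would show 8 × (1 − f): 8.0, 7.2, 6.0 or 4.0 for f = 0, 10%, 25% or 50%. At f = 0 nothing is lost.

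**3. What does a by-time-point percentage say about patients ever affected?** Assume 3% beyond the limit at each of 21 times, with all patients sampled each time:

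- always the same patients: 3%
- independent between times: 1 − 0.97^21 = 47%
- different patients each time: 21 × 3% = 63%

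This third gap exists even if no additional draw is ever taken.

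**The case against.** The strongest reply has four parts.

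- **Other routes exist.** The values are listed, and for iCa, pH, anion gap and base excess they enter the MMRM. Hypocalcemia and metabolic acidosis are on the anticipated list in Protocol 6.10.6 and are tabulated per patient as AEs. This stands against any inference that off-schedule values are lost altogether. It does not close the gap: a mean model does not count crossings, the ratio has no model, citrate accumulation is not on the anticipated list, and AE terms do not reproduce a count at 2.1.
- **Rechecks add no patient.** If the first abnormal value came from a scheduled draw, the patient is already in the table. This stands. What remains is the peak value seen on a recheck and any excursion first seen off schedule.
- **The scope of SAP 8.5 is unclear.** SAP 13.3 mentions the frequencies separately from the descriptive summary, so the threshold tables may not be covered by the exclusion. The ambiguity is real, but a table by scheduled time point has no cell for an unscheduled value on either reading.
- **Scheduled-only tables are defensible.** In an open-label trial, clinician-initiated sampling may differ by arm, and a count from all draws then carries ascertainment bias. This stands, and is a reason to show both counts.

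A reader might also infer that the loss falls on the Prismocitrate arm alone. The documents do not support that. Protocol 5.2.3 applies the citrate-accumulation monitoring to all study patients, and only the Prismocitrate rate change and infusion stop are specific to one arm. More extra draws in that arm are plausible but not stated. Nor can one infer that two-thirds of excursions go unreported. The two hours in Protocol 5.2.3 are the time allowed for improvement after a response; they neither order a draw at two hours nor limit how long an undetected excursion lasts.

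**Conclusion.** The point holds as a gap in safety reporting. A ratio above 2.1 seen only on an additional draw reaches a listing but no laboratory table, apart from the possible end-of-study substitution. For all five limits, the number of patients who ever crossed cannot be read from the planned tables and can be understated.

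The size is unknown, because the documents give no event rates, excursion durations or numbers of additional draws; it could be zero. The conclusion rests on reading the threshold tables as confined to scheduled times, which their layout indicates. The primary analysis is not affected. The change is worth making because the ratio is a named measure of the main metabolic risk and the data are already in hand.

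**What to change.** 1. **SAP 8.5:** define an additional draw, including how out-of-window scheduled samples are treated, and limit the exclusion to by-time-point summaries.
2. **SAP 13.3 and 14.3, Tables 14.2.12.1 to 14.2.12.5:** for each existing limit, add the number and percentage of patients with at least one value beyond it at any time during study CRRT, and the patient's worst value (highest ratio and anion gap; lowest iCa, pH and base excess). Report by actual treatment, as SAP 14 sets for safety. SAP 13.3 groups iCa by randomized arm, so the iCa row should state its grouping.
3. **Show two counts side by side:** scheduled draws only, and all draws.

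The cost is SAP wording and a few rows in existing tables. No new data and no change to clinical rules are needed. The downside is that the all-draw count will look worse in whichever arm is sampled more often. The scheduled-only count beside it makes that visible, and Protocol 7.4.9 already collects the number of iCa determinations in both arms, which can be reported with it.
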